7.3 Exclusion Criteria

Potential subjects meeting any of the following criteria will be excluded:

1. Known history and/or presence of any clinically significant hepatic (e.g., hepatitis, jaundice, hepatic failure, hepatic necrosis, hepatic encephalopathy, biliary tract diseases, cirrhosis), renal/genitourinary (e.g., urethral stricture, any renal impairment), gastrointestinal, cardiovascular (e.g., hypotension including orthostatic hypotension, cor pulmonale, congenital long QT, congestive heart failure, brady arrhythmias), cerebrovascular, pulmonary (e.g., chronic obstructive pulmonary disease, decreased respiratory reserve, hypoxia, pre-existing respiratory depression), endocrine (e.g., myxedema, hypothyroidism, adrenal cortical insufficiency), immunological, musculoskeletal (e.g., kyphoscoliosis), neurological (e.g., CNS depression or coma, increased cerebrospinal pressure), psychiatric (e.g., psychosis, depression, hallucinations, delirium tremens, suicidal thoughts or behavior), dermatological or hematological (e.g., thrombocytopenic purpura) disease or condition unless determined as not clinically significant by the PI/Sub-Investigator.
2. History or presence of any clinically significant gastrointestinal pathology (e.g., chronic diarrhea, inflammatory bowel disease), unresolved gastrointestinal symptoms (e.g., diarrhea, vomiting), or other conditions known to interfere with the absorption, distribution, metabolism or excretion of the drug experienced within 7 days prior to first tacrolimus administration, as determined by the PI/Sub-Investigator.
3. Systolic blood pressure outside 90-130 mmHg, inclusive, and diastolic blood pressure outside 55-80 mmHg, inclusive, and heart rate between 50-100 bpm, inclusive, unless deemed otherwise by the PI/Sub-Investigator.
4. QTc interval \geq 440 milliseconds for males and \geq 460 milliseconds for females, unless deemed otherwise by the PI/Sub-Investigator.
5. Abnormal clinical laboratory values unless values are deemed by the PI/Sub-Investigator as "Not Clinically Significant".
6. Abnormal vital signs (blood pressure [BP], heart rate [HR], respiratory rate [RR], pulse oximetry and temperature) measurements, unless deemed otherwise by the PI/Sub-Investigator.

7. Presence of any clinically significant illness within 30 days prior to first dosing, as determined by the PI/Sub-Investigator.
8. Presence of any significant physical or organ abnormality as determined by the PI/Sub-Investigator.
9. A positive test result for any of the following: HIV, Hepatitis B surface antigen, Hepatitis C, drugs of abuse (marijuana, amphetamines, barbiturates, cocaine, opiates, phencyclidine and benzodiazepines), and alcohol test. Positive serum or urine pregnancy test for female subjects.
10. Known history or presence of:
 - Alcohol abuse or dependence within one year prior to first study drug administration;
 - Drug abuse or dependence;
 - Hypersensitivity or idiosyncratic reaction to tacrolimus, its excipients, and/or related substances;
 - Lymphoma and other malignancies (particularly of the skin);
 - Bacterial, viral, fungal and protozoal infections (e.g., polyoma virus-associated nephropathy [PVAN] due to BK virus infection, JC virus associated progressive multifocal leukoencephalopathy [PML], Epstein Barr Virus (EBV) associated Post transplant lymphoproliferative disorder [PTLD], cytomegalovirus (CMV) infections associated CMV viremia and CMV disease);
 - Tuberculosis;
 - Posterior reversible encephalopathy syndrome (PRES);
 - Pure red cell aplasia (PRCA);
 - Gastrointestinal perforation;
 - Hyperkalemia;
 - Hypertension;
 - Lactose intolerance, galactose intolerance, Lapp lactase deficiency or glucose-galactose malabsorption;
 - Food allergies and/or presence of any dietary restrictions unless deemed by the PI/Sub-I as “Not Clinically Significant”.
 - Severe allergic reactions (e.g. anaphylactic reactions, angioedema).
11. History of intolerance to and/or difficulty with blood sampling through venipuncture.

12. Abnormal diet patterns (for any reason) during the four weeks preceding the study, including fasting, high protein diets, vegan, etc.
13. Individuals who have donated, in the days prior to first tacrolimus administration:
 - 50-499 mL of blood in the previous 30 days;
 - 500 mL or more or double red blood cell (“Power red”) donation in the previous 56 days.
14. Donation of plasma by plasmapheresis within 7 days prior to first tacrolimus administration.
15. Hemoglobin level of 12.0 g/dL or lower.
16. Individuals who have participated in another clinical trial or who received an investigational drug within 30 days prior to first tacrolimus administration.
17. Not being able to fast for at least 14 hours.
18. Consumption of food or beverages containing grapefruit and/or pomelo within 3 days prior to first study drug administration.
19. Consumption of food or beverages containing caffeine/methylxanthines, poppy seeds and/or alcohol within 48 hours before dosing in each study period.
20. Use of any prescription medication within 14 days prior to first tacrolimus administration (except for allowed contraceptive products).
21. Use of any over-the-counter medications (including low-dose aspirin, oral multivitamins, allergy medications, herbal and/or dietary supplements) within 14 days prior to first tacrolimus administration (except for spermicidal/barrier contraceptive products).
22. Use of any enzyme-modifying drugs and/or other products, including inhibitors of cytochrome P450 (CYP) enzymes such as antifungals (e.g., ketoconazole, itraconazole, fluconazole, voriconazole, posaconazole, clotrimazole), macrolide antibiotics (e.g., erythromycin, clarithromycin, josamycin), protease inhibitors (e.g., ritonavir, telaprevir [Incivek™], boceprevir [Victrelis™], nelfinavir [Viracept®], saquinavir), calcium channel blockers (e.g., verapamil, diltiazem, nifedipine, nicardipine), nucleotide reverse transcriptase inhibitors (e.g., tenofovir), gastric acid suppressors/neturalizers (e.g., lansoprazole, omeprazole, cimetidine, cisapride, magnesium-aluminum hydroxide antacids), bromocriptine, cortisone, dapsone, ergotamine, gestodene, lidocaine, mephenytoin, miconazole, midazolam, nilvadipine, quinidine, tamoxifen, and triacetyl-oleandomycin and inducers of CYP enzymes such as anti-myobacterials (e.g., rifampin, rifabutin), antifungal agent (e.g., caspofungin), anticonvulsants (e.g. phenytoin, carbamazepine, phenobarbital),

corticosteroids (e.g. prednisolone or methylprednisolone), metamizole, isoniazid and products containing St. John's Wort in the previous 30 days before first study drug administration.

23. Use of medicines such as, mycophenolic acid (MPA) products, aminoglycosides, gyrase inhibitors, vancomycin, cotrimoxazole, NSAIDs, oral anticoagulants, or oral antidiabetics, ganciclovir, acyclovir, amphotericin B, ibuprofen, cisplatin, potassium supplements, potassium-sparing diuretics (e.g., amiloride, triamterene or spironolactone), ACE inhibitors (for example, benazepril, enalapril, quinapril), statins (for example, atorvastatin, fluvastatin, simvastatin), angiotensin receptor blockers (for example, irbesartan, valsartan, azilsartan), nefazodone, metoclopramide, danazol, and herbal products containing *Schisandra sphenanthera* extracts should be avoided during treatment with tacrolimus in the previous 30 days before first study drug administration.
24. Use of any QT prolonging drugs (e.g., citalopram, chlorpromazine, haloperidol, methadone), amiodarone [Cordarone™, Nexterone™, Pacerone™], immunosuppressive or immunomodulating therapies (e.g. sirolimus [Rapamune®], cyclosporins [Gengraf®, Neoral®, and Sandimmune®], antilymphocytic antibodies [e.g., basiliximab, daclizumab]) should be avoided during treatment with tacrolimus in the previous 30 days before first study drug administration.
25. Individuals having undergone any major surgery within 6 months prior to the start of the study, unless deemed otherwise by PI/Sub-Investigator.
26. Does not agree, to refrain from driving or operating heavy machinery if feeling dizzy or drowsy following tacrolimus administration until full mental alertness is regained.
27. Does not have an ability to fast for at least 14 hours.
28. Recent history (within 8 weeks prior to screening) of travel to or emigration from any country with high incidence of tuberculosis.
29. Temperature at visit is ≥ 100.4 F (38.0° C).
30. Test positive for SARS-CoV-2 by locally available, verified test.
31. Have had common symptoms of COVID-19 currently or in the past 14 days as documented in the COVID-19 screening questionnaire and symptom checklist
32. Have had an exposure to suspected or confirmed cases of COVID-19 in the past two weeks as documented in the COVID-19 screening questionnaire

33. Recent live attenuated vaccine¹ recipients in the past month.

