8.6 Vital Signs

Vital signs (BP and HR) will be monitored at pre-dose and at 1, 2, 4, 6, 12-, 24-, 48- and 72-hours post-dose in each study period.

Pre-Dose and Post-Dose (all periods):

Acceptable Range - systolic blood pressure between 90-130 mmHg, diastolic blood pressure between 55-80 mmHg, inclusive, and heart rate between 50-100 bpm, inclusive.

If the Investigator is not immediately available on site to assess out of range vital signs, the vital signs will be repeated up to two times. If vital signs are still outside of the acceptable range, the PI/Sub-Investigator will be informed, and PI/Sub-Investigator will determine the appropriate course of action.

Additional vital signs measurements will be taken if deemed necessary by the PI/Sub-Investigator. Blood draws will take precedence over vital signs measurements and other scheduled activities if the scheduled time of several activities is overlapped to each other unless deemed necessary by the PI/Sub-Investigator or due to subject's safety.

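### Exclusion criterion 3 states the heart-rate limit the wrong way round, making 50-100 bpm a ground for exclusion

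*Combined protocol and SAP*

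**What the plan says.** The lead-in to section 7.3 makes every item a reason to exclude: "Potential subjects meeting any of the following criteria will be excluded".

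Item 3 then gives three limits in one sentence: "Systolic blood pressure outside 90-130 mmHg, inclusive, and diastolic blood pressure outside 55-80 mmHg, inclusive, and heart rate between 50-100 bpm, inclusive". It ends by letting the investigator decide otherwise.

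Section 8.6, under the label "Pre-Dose and Post-Dose (all periods", sets out the range that is acceptable: "Acceptable Range - systolic blood pressure between 90-130 mmHg, diastolic blood pressure between 55-80 mmHg, inclusive, and heart rate between 50-100 bpm, inclusive".

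Item 6 of section 7.3 is a general criterion without numbers: "Abnormal vital signs (blood pressure [BP], heart rate [HR], respiratory rate [RR], pulse oximetry and temperature) measurements, unless deemed otherwise by the PI/Sub-Investigator".

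**The concern.** Item 3 uses 'outside' for systolic and diastolic pressure and switches to 'between' for heart rate. In a list of exclusions, that makes a normal heart rate count towards exclusion, while a slow or fast one does not.

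Item 3 also holds the only numerical blood-pressure and heart-rate limits stated for screening. Section 5.1.1 has both measured at screening but sets no limits, item 6 has no numbers, and the section 8.6 range is labelled for use before and after dosing. Staff who see the slip must therefore depart from the literal criterion and supply a heart-rate limit that the protocol does not state for that visit.

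What is at stake is consistent, auditable screening of healthy volunteers. The pharmacokinetic analysis is not involved.

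**Working it through.** No arithmetic applies. The check sets the texts side by side and then applies item 3 to example volunteers.

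**Direction of each limit**

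| Measurement | Item 3 excludes when | Section 8.6 accepts | Consistent? |
|---|---|---|---|
| Systolic pressure | outside 90-130 mmHg | 90-130 mmHg | yes |
| Diastolic pressure | outside 55-80 mmHg | 55-80 mmHg | yes |
| Heart rate | within 50-100 bpm | 50-100 bpm | no, inverted |

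The figures agree in all three rows. Only the direction of the heart-rate limit differs, so 1 of 3 limits is inverted. The matching blood-pressure rows show which direction was intended.

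**What item 3 does as written**

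The 'and' connectors allow two readings. On the list reading, meeting any one limit excludes. On the joint reading, all three must be met. The intended rule is taken to be exclusion when any measurement lies outside its section 8.6 range. The waiver is left aside.

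| Volunteer | List reading | Joint reading | Intended rule |
|---|---|---|---|
| Both pressures in range, 70 bpm | excluded | not excluded | not excluded |
| Both pressures in range, 45 bpm | not excluded | not excluded | excluded |
| Both pressures in range, 110 bpm | not excluded | not excluded | excluded |
| Systolic 150 mmHg, diastolic in range, 70 bpm | excluded | not excluded | excluded |
| Both pressures out of range, 70 bpm | excluded | excluded | excluded |
| Both pressures out of range, 110 bpm | excluded | not excluded | excluded |

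The list reading makes every normal heart rate an exclusion that needs a waiver. The joint reading excludes only someone with both pressures out of range and a normal heart rate. Neither reproduces the intended rule, and on neither does item 3 exclude a volunteer whose only abnormality is 45 or 110 bpm.

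Item 4 uses 'and' as a list connector in its QTc limits ("440 milliseconds for males and", followed by the limit for females). This is weak support for the list reading, because males and females are separate groups while one volunteer has all three of the item 3 measurements. The finding does not depend on which reading is chosen.

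**Other numerical limits that apply at screening**

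Respiratory rate (12 to 20 per minute) and pulse oximetry (at least 95%) have normal ranges in section 8.5.4, which names screening. Temperature has an upper limit in item 29 (100.4 F or higher excludes). Blood pressure has item 3, in the right direction, subject to how 'and' is read. Of the five vital signs named in item 6, heart rate is the one whose only stated screening limit points the wrong way.

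**What else would stop an abnormal heart rate**

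- Item 6 excludes it by default; judgement is needed only to waive.
- Item 1 covers clinically significant disease, including "cardiovascular (e.g., hypotension including orthostatic hypotension, cor pulmonale, congenital long QT, congestive heart failure, brady arrhythmias".
- Item 10 lists "Hypertension", which is a backstop for pressure, not for heart rate.
- Inclusion criterion 3 requires good health judged partly on vital signs.
- Section 2.0 has eligibility reassessed at Period 1 check-in.
- The section 8.6 range applies before the first dose. If the investigator is not immediately on site, an out-of-range reading is repeated up to twice and then referred to the investigator, who decides what to do. It is not an automatic exclusion.

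**The case against.** The strongest reply is that this is a typographical slip that corrects itself. No site running a healthy-volunteer study would exclude people for having a normal heart rate, and item 3 carries a waiver in any case. Item 6 already excludes abnormal rates. The revision history refers to the section 8.6 figures as normal ranges, which gives 'abnormal' in item 6 a natural meaning, and item 3 repeats the same blood-pressure figures. On the joint reading, heart rate alone excludes nobody. The phrase 'outside ..., inclusive' is most naturally read as placing the endpoints within the acceptable range.

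Much of this stands, and it settles the severity. Staff would very probably apply the intended limit, and borrowing the section 8.6 range at screening is an easy inference. The endpoint wording is a minor point.

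It does not make the criterion right. Item 3 is an operative eligibility rule, and every defence of it relies on not following its words. A waiver is meant for exceptions and does not correct a limit that points the wrong way. The joint reading removes the perverse exclusion of normal heart rates only by leaving item 3 almost without effect, including for blood pressure. None of the backstops states a heart-rate number for screening.

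**Conclusion.** The concern holds. The heart-rate limit in item 3 is inverted, and the 'and' connectors are a secondary fault. This rests on the current text of sections 7.3 and 8.6 and on one assumption: that the section 8.6 range is what item 3 was meant to enforce. The identical blood-pressure figures support that assumption.

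The severity is low; this is a correction to consider at the next amendment. Item 6 does the protective work by default. The sample size is also unaffected.

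**What to change.** Reword item 3 along these lines: 'Systolic blood pressure below 90 or above 130 mmHg, or diastolic blood pressure below 55 or above 80 mmHg, or heart rate below 50 or above 100 bpm', followed by the existing waiver clause.

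This turns the heart-rate limit the right way, removes the 'and' ambiguity, and makes all six boundary values (90, 130, 55, 80, 50 and 100) clearly acceptable, in line with section 8.6. Compared with the joint reading, 'or' widens the blood-pressure exclusion, so the investigator and sponsor should confirm both the limits and the connector.

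The cost is one reworded criterion. Section 15.1 treats typographical corrections as administrative changes that go to the IRB but may not need its approval. Because the connector change could be seen as more than typographical, the sponsor should decide which route applies. Study procedures do not change.

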7.4 Informed Consent Procedure

The Investigator will be responsible for ensuring that the informed consent is obtained before any protocol specific procedures are carried out. The decision of a subject to participate in clinical research is voluntary and will be based on a clear understanding of what is involved.

Subjects will receive adequate oral and written information. The oral explanation to the subject will be performed by the Investigator or a designated person and will cover all the elements specified in the informed consent form.

The subject will be given every opportunity to clarify any points they do not understand and, if necessary, to ask for more information. The subject will be given sufficient time to consider the provided information. It will be emphasized that the subjects may withdraw their consent to participate at any time without loss of benefits to which they otherwise would be entitled.

The subjects will be informed that all attempts to maintain confidentiality will be made. Their names or personally identifiable information will not be disclosed outside the site. The Investigator or delegated member of the trial team and the subject will sign and date the Informed Consent Form (ICF) to confirm that consent has been obtained. The subject will receive a copy of this document and the original will be filed in the subject binder. In case of a screen failure, it will be filed separately in the designated binder.

7.5 Study Restrictions

If at any time prior to or during the study, any subject does not comply with the restrictions mentioned below, the subject's continued participation will be re-assessed by the PI/Sub-Investigator, Pharmacokinetic staff, and reported to the Sponsor.

1. No food will be allowed from at least 10 hours before dosing until at least 4 hours after dosing. Except for the 8 ± 0.1 fl. oz. water given with study medication, no fluid will be allowed from 1 hour before dosing until 1-hour post-dose. Water will be allowed/provided *ad libitum* at all other times.
2. No smoking will be permitted during confinement.
3. Subjects will be required not to drive or operate heavy machinery as indicated in [Section 7.3](#).

¹ Adenovirus Type 4 and Type 7 vaccine (Oral), Cholera vaccine, Ebola Zaire vaccine (Live), Influenza vaccine, Measles, Mumps, and Rubella Virus Vaccine (Live), Smallpox (Vaccinia) Vaccine (Live), Smallpox and Monkeypox vaccine (Live, Non-replicating), Typhoid Vaccine (Live Oral Ty21a), Yellow Fever Vaccine and Zoster Vaccine (Live).

4. Subjects will be required to limit exposure to sunlight and UV light by wearing protective clothing and using a sunscreen with a high protection factor during study participation until the study completion.
5. Subjects will be required not to receive a vaccination (live attenuated vaccine). Examples include (but are not limited to): Adenovirus Type 4 and Type 7 vaccine (Oral), Cholera vaccine, Ebola Zaire vaccine (Live), Influenza vaccine, Measles, Mumps, and Rubella Virus Vaccine (Live), Smallpox (Vaccinia) Vaccine (Live), Smallpox and Monkeypox vaccine (Live, Non-replicating), Typhoid Vaccine (Live Oral Ty21a), Yellow Fever Vaccine and Zoster Vaccine (Live) during the study and until 30 days after the study has ended (last study procedure).
6. The consumption of alcohol of any kind (e.g., wine, beer, liquor, cocktails), products containing caffeine/methylxanthines (e.g., coffee, tea, chocolate, caffeine-containing soft drinks [e.g. Coke, Pepsi, Red Bull]) and poppy seeds containing products (poppy seed cake, cookies, bagels) will be prohibited for 48 hours prior to tacrolimus administration until after the last blood draw in each study period.
7. The consumption of foods and/or beverages containing grapefruit and/or pomelo (e.g., grapefruit, grapefruit juice, grapefruit candies, pomelo, etc.) will be prohibited for 3 days prior to first tacrolimus administration until the last blood draw in the final study period.
8. Any concomitant medication (prescription medications [e.g., prescription pills, topical systemic creams, inhalants, sprays] or over-the-counter such as low-dose aspirin, allergy medications and oral multivitamins), any herbal and/or dietary supplements will not be permitted for 14 days prior to first drug administration.
9. Any concomitant medication (prescription medications [e.g., prescription pills, topical systemic creams, inhalants, sprays] or over-the-counter), any herbal and/or dietary supplements from the start of dosing of the study until the last blood draw in the final study period unless deemed otherwise by the PI/Sub-Investigator for treatment of any adverse events (AEs).

Any use of concomitant medication or herbal/dietary supplement during the restriction period for the restriction # 9 will be reported as soon as possible to the PI/Sub-Investigator, Pharmacokinetic staff and reported to the Sponsor. In each case, the decision whether to continue or discontinue the subject's participation in the study will be made by the PI/Sub-Investigator and/or by the Pharmacokinetic staff and reported to the Sponsor.

10. Use of any enzyme-modifying drugs and/or other products, including inhibitors of cytochrome P450 (CYP) enzymes such as antifungals (e.g., ketoconazole, itraconazole, fluconazole, voriconazole, posaconazole, clotrimazole), macrolide antibiotics (e.g., erythromycin, clarithromycin, josamycin), protease inhibitors (e.g., ritonavir, telaprevir [IncivekTM], boceprevir [VictrelisTM], nelfinavir [Viracept[®]], saquinavir), calcium channel blockers (e.g., verapamil, diltiazem, nifedipine, nicardipine), nucleotide reverse transcriptase inhibitors (e.g.,

tenofovir), gastric acid suppressors/neutralizers (e.g., lansoprazole, omeprazole, cimetidine, cisapride, magnesium-aluminum hydroxide antacids), bromocriptine, cortisone, dapsone, ergotamine, gestodene, lidocaine, mephenytoin, miconazole, midazolam, nilvadipine, quinidine, tamoxifen, and triacetyl-oleandomycin and inducers of CYP enzymes such as anti-myobacterials (e.g., rifampin, rifabutin), antifungal agent (e.g., caspofungin), anticonvulsants (e.g., phenytoin, carbamazepine, phenobarbital), corticosteroids (e.g., prednisolone or methylprednisolone), metamizole, isoniazid and products containing St. John's Wort within 30 days prior to first study drug administration until the last blood draw in the final study period.

11. Use of medicines such as, mycophenolic acid (MPA) products, aminoglycosides, gyrase inhibitors, vancomycin, cotrimoxazole, NSAIDs, oral anticoagulants, or oral antidiabetics, ganciclovir, acyclovir, amphotericin B, ibuprofen, cisplatin, potassium supplements, potassium-sparing diuretics (e.g., amiloride, triamterene or spironolactone), ACE inhibitors (for example, benazepril, enalapril, quinapril), statins (for example, atorvastatin, fluvastatin, simvastatin), angiotensin receptor blockers (for example, irbesartan, valsartan, azilsartan), nefazodone, metoclopramide, danazol, and herbal products containing *Schisandra sphenanthera* extracts should be avoided during treatment with tacrolimus within 30 days prior to first study drug administration until the last blood draw in the final study period.
12. Use of any QT prolonging drugs (e.g., citalopram, chlorpromazine, haloperidol, methadone), amiodarone [Cordarone™, Nexterone™, Pacerone™], immunosuppressive or immunomodulating therapies (e.g., sirolimus [Rapamune®], ciclosporins [Gengraf®, Neoral®, and Sandimmune®], antilymphocytic antibodies [e.g., basiliximab, daclizumab]) should be avoided during treatment with tacrolimus within 30 days prior to first study drug administration until the last blood draw in the final study period.
13. Physical activity: Subjects will remain awake for the first 4 hours following tacrolimus administration. If a medical event (i.e., AE) occurs, subjects may be placed in an appropriate position at that time. Subjects will be required to abstain from strenuous/vigorous activities for the duration of the study period(s). When the subjects leave the clinic, they will be requested to refrain from strenuous physical activity until the completion of the 144-hour blood draw in each study period.
14. For 3 hour after each study drug administration, subject visits to the washroom will be monitored and recorded by clinic staff. Subjects will be restricted from flushing the toilet to allow staff to inspect the content during this time.
15. Additional study restriction for COVID-19 prevention and control:
 - Subjects must be willing to social distance, wear masks and practice hand hygiene while enrolled in the study

- Report to study staff in case of exposures to known or possible COVID-19 positive cases during the study

